Obese patients have a high risk of difficult laryngoscopy due to their short, thick neck, large tongue, and significant redundant pharyngeal soft tissue.¹¹ However, till now there is no established predictor for difficult intubation in obese patients. One study reported a correlation between oropharyngeal Mallampati score and BMI as predictors of difficult laryngoscopy.²⁴ However, another study showed BMI was not associated with difficult intubation in obese patients.²⁵ Although Mallampati score may predict potential intubation difficulties, intubation by direct laryngoscopy was successful in 99% patients.²⁵ Other investigators demonstrated that Mallampati score had low specificity (62%) and low positive predictive values (29%) for difficult intubation.²⁶ Interestingly, an abundance of pretracheal soft tissue measured ultrasonically and neck circumferences may predict difficult laryngoscopy.^{27,28}

Difficult Arterial Cannulation

The common cardiovascular comorbidities present in obese patients frequently necessitate continuous arterial pressure monitoring in surgery.²⁹ However, it is more difficult for clinicians to perform an arterial catheterization in obese patients due to their excessive subcutaneous tissue. Besides, obese patients tend to have a higher risk of vascular complication after arterial catheterizations.¹⁶ Therefore, strategy to increase the success rate of arterial cannulation and reduce potential vascular complications becomes an important issue for obese surgical patients.

Ultrasound guidance has emerged as a useful tool for central vein catheterization with the advantages of higher success rate, patient safety, and cost-effectiveness.³⁰ For radial artery catheterization, ultrasound guidance is also an effective and safe technique, especially in pediatric population.³¹⁻³³ For resident physicians, ultrasound achieved significantly faster placement of the arterial lines, fewer attempts, and fewer catheters used.³⁴ However, the effectiveness and safety of ultrasound-guided arterial catheterization have not been investigated in obese patients. Besides, ultrasound offers the most accurate measurement for thickness of subcutaneous adipose tissue layers.³⁵ The distance from skin surface to commonly-catheterized arteries (e.g. radial artery, brachial artery, and femoral artery) has not been explored in obese patients.

Preoxygenation Strategy to Prevent Desaturation

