Before surgery, the investigators will use a portable ultrasound device (LOGIQ™, GE Healthcare, Chicago, IL, USA) to measure the skin-to-artery distance of common sites of arterial cannulation of all enrolled patients, including radial artery, brachial artery, and dorsalis pedis artery. Patients will be randomized in a ratio of 1:1 into ultrasound group (N=40) or palpation group (N=40). Radial artery cannulation will be performed using a radial artery catheterization kit (Arrow International Inc, Reading, PA, USA). For all patients, the wrist will be extended and taped to a board to maintain wrist extension, and the skin near the puncture site will be cleaned with chlorhexidine according to standard protocol. Allen test will be used to assess the vascular patency of the hand before cannulation of the radial artery.⁶⁰ All patients will receive local skin anesthesia at the anticipated puncture site. All radial artery catheterizations will be performed by trained year 1 or 2 anesthesiology residents with similar levels of experience in both blind-palpation and ultrasound-guided radial arterial catheterization. All residents have performed at least 5 blind-palpation and 5 ultrasound-guided radial arterial catheterizations prior to the study.

In the ultrasound group, a linear vascular probe in the frequencies 5 to 13 MHz (GE 12L-RS, GE Healthcare, Chicago, IL, USA) of portable ultrasound device (LOGIQ™, GE Healthcare, Chicago, IL, USA) will be applied to the skin to localize the radial artery and a 20-gauge catheter will be inserted distal to the transducer and directed according to the ultrasound image. Start time is defined as the time when the ultrasound probe is placed on the wrist. In the palpation group,

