the radial artery will be identified by palpation, and the cannula will be directed by continuous or intermittent palpation of arterial pulsation. The attending anesthesiologist will supervise the resident and act as the second operator if needed. An attempt is defined as a new penetration of the skin with the needle, followed by an unlimited number of subcutaneous needle redirections. Clinical judgment by the supervising anesthesiologist is used to determine the time allowed for an attempt, number of attempts allowed, and changes to a new site. The attending anesthesiologist will take over arterial cannulation if residents perform for more than 3 times or > 15 minutes. The start time is defined when the operator's finger is initially placed on the patient's wrist. The end point for both methods is when the arterial catheter is successfully placed. Primary outcome is first-attempt success rate, and secondary outcomes comprise time to successful arterial catheterization, number of attempts, sites and catheters used. Complications related to arterial cannulation will also be recorded, including pain, hematoma formation, and arterial vasospasm or occlusion.

Substudy 3. Comparing the effectiveness of preoxygenation between HFNC and facemask: A single-blind randomized controlled trial

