The distributions of baseline patient characteristics and outcome variables will be compared between two groups using chi-square tests or Fisher's exact test for categorical variables and either t tests or Wilcoxon rank sum tests for continuous variables, as appropriate. For four-group comparisons, either ANOVA tests or Kruskal-Wallis tests will be used for continuous variables, as appropriate. A Bonferroni correction to the significance criterion for multiple comparisons is applied where appropriate. For time to event data, Kaplan-Meier method and log-rank test will be applied for group comparisons. Multivariable logistic regression, simple linear regression, or Cox proportional hazards regression analyses will be used to identify potential influential factors of outcomes of interest. A two-sided significance level of 0.05 was used to define statistically significant difference. All the statistical analyses will be conducted using Statistics Analysis System (SAS), Version 9.4 (SAS Institute Inc., Cary, NC, USA).

According to prior study³⁷, at least 37 patients in each group of HFNC or facemask preoxygenation are needed to detect a difference of 30 seconds of nonhypoxic apnea time between the HFNC and facemask group, accepting a type I error of 5% and type II error of 20% with anticipated nonhypoxic apnea time of mean $188 \pm SD 46$ seconds in the facemask group.⁶⁵ Nevertheless, in order to allocate 20 patients into each group of volatile anesthesia with desflurane or sevoflurane with or without M-Entropy guidance, a total of 80 patients will be enrolled in this study.

TMU-JIRB Form059/20180201
Protocol Number: N202002076
Version : 4
Date : 2020.04.08

There are about 120 patients undergoing LSG at our hospital per year. Considering the patient selection criteria and possible patient refusal, a total of 50 patients per year will be enrolled in this study. Therefore, it will take about 2 years for patient recruitment. Besides, the investigators will select all randomized subjects for analysis.

Reference

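### Substudy 2 measures radial skin-to-artery distance in every patient, but the only between-arm test given for first-attempt success leaves it out, at a possible cost in power

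*Combined protocol and SAP*

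**What the plan says.** Under Substudy 2, the investigators will use portable ultrasound before surgery "to measure the skin-to-artery distance of common sites of arterial cannulation of all enrolled patients": radial, brachial and dorsalis pedis. Patients are allocated 1:1, 40 to ultrasound and 40 to palpation. "Primary outcome is first-attempt success rate"; the distance is in neither the outcome list nor the complication list.

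The background section on difficult arterial cannulation says that "it is more difficult for clinicians to perform an arterial catheterization in obese patients due to their excessive subcutaneous tissue". It then describes ultrasound as the best way to measure fat thickness, and says that the distance from skin to the commonly cannulated arteries "has not been explored in obese patients".

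The Statistical Analysis Plan section is one set of rules for all four substudies. Baseline characteristics and outcomes are compared between two groups "using chi-square tests or Fisher's exact test for categorical variables". Later it adds: "Multivariable logistic regression, simple linear regression, or Cox proportional hazards regression analyses will be used to identify potential influential factors of outcomes of interest". It names no covariates, does not mention skin-to-artery distance, and does not say that a treatment effect will be taken from such a model. Randomisation uses permuted blocks, with no stratification factor stated.

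**The concern.** A baseline measurement is planned for everyone, it bears on the protocol's own account of why cannulation is hard in these patients, and no analysis is assigned to it. If depth does predict first-attempt failure, leaving it out of the between-arm comparison gives away power in a small substudy and leaves chance differences in depth between arms unadjusted.

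Prespecification is also at stake. Substudy 2 is open-label, and the regression sentence leaves the covariates open. An adjusted analysis chosen after the data are seen would carry less weight than one fixed now.

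**Working it through.** **The plan's own calculation.** The only sample-size calculation is for Substudy 3: a 30 s difference, SD 46 s, two-sided 5%, 80% power.

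n per group = 2 × 46² × (1.960 + 0.842)² / 30² = 2 × 2116 × 7.85 / 900 = 36.9, so 37.

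This reproduces the stated 37, but it concerns nonhypoxic apnea time and says nothing about Substudy 2. The total of 80 was set to fill Substudy 4's four groups of 20.

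**What 40 per arm gives Substudy 2, unadjusted.** Success rates are assumptions, because the documents give none.

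Power = Φ{(d√n − 1.96√(2p̄(1−p̄))) / √(p₁(1−p₁) + p₂(1−p₂))}

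For 50% vs 80%, p̄ = 0.65: (0.30 × 6.325 − 1.96 × 0.6745) / 0.640 = 0.575 / 0.640 = 0.90, so power is about 82%. On the same formula, 80% power needs differences of about 31, 30, 27 and 24 percentage points at palpation success of 40%, 50%, 60% and 70%. The substudy has little power to spare.

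**Chance imbalance.** The standard error of a standardised difference in mean depth is √(2/40) = 0.22. The arms differ by more than 0.3 SD with probability 2{1 − Φ(0.3/0.224)} = 2{1 − Φ(1.34)}, about 18%.

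**Gain from adjusting, conditional effect fixed.** Simulated trials, 40 per arm, arm log-odds effect 1.4 (50% vs 80% at average depth), one standardised baseline covariate, 2,000 trials per setting (Monte Carlo error about 1 point). The depth slopes are assumptions; 0.5, 0.9 and 1.3 per SD are odds ratios of about 1.6, 2.5 and 3.7.

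| How depth acts | Slope per SD (log-odds) | Unadjusted | Adjusted |
|---|---|---|---|
| Not prognostic | 0 | 82.2% | 81.7% |
| Same slope in both arms | 0.5 | 81% | 83% |
| Same slope in both arms | 0.9 | 72% | 80% |
| Same slope in both arms | 1.3 | 62% | 74% |
| Half the slope under ultrasound | 0.9 | 79.4% | 82.2% |
| Half the slope under ultrasound | 1.3 | 78.1% | 84.4% |
| Palpation arm only | 0.5 | 84.0% | 84.6% |
| Palpation arm only | 0.9 | 83.4% | 85.1% |
| Palpation arm only | 1.3 | 84.0% | 85.7% |

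**Gain from adjusting, overall success rates fixed.** With the conditional effect held at 1.4, a steeper slope shrinks the overall difference between arms, which accounts for the fall in unadjusted power from 81% to 62%. A second simulation (3,000 trials, chi-square vs likelihood-ratio test, same slope in both arms) therefore fixed the overall rates. At 50% vs 80% the results were 82% vs 83%, 82% vs 86%, 82% vs 89% and 81% vs 93% at odds ratios per SD of 1.5, 2, 3 and 5. Across this and two other pairs of rates (50% vs 75%, 60% vs 85%), the gains were 1–2, 4–5, 7–10 and 12–15 points. The gain is therefore not an artefact of the first set-up.

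**Type I error.** With no treatment effect, both tests rejected in about 5–6% of trials.

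**The case against.** The best defence is that nothing here is an error. Allocation is randomised, the unadjusted comparison is valid, and its type I error matches that of the adjusted test. That stands: a reader might infer that an imbalance in depth would bias the result, but the documents and the simulations support only a loss of precision.

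Second, a reader might infer that the plan names chi-square as Substudy 2's primary analysis and excludes adjustment. It does neither. The testing rule is generic, Fisher's exact test is an alternative, and the multivariable logistic regression could hold both arm and distance. This narrows the point but does not remove it. No covariate is named, the stated purpose is factor-finding, and no other between-arm comparison is offered for this outcome.

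Third, depth is not shown to be a strong predictor. The protocol blames subcutaneous tissue and calls the distance unexplored in obese patients. Measuring the brachial and dorsalis pedis arteries too suggests a descriptive aim. The link to first-attempt success is a reasonable inference, and its strength is unknown.

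Fourth, if ultrasound works by making depth irrelevant, the main-effect gain almost vanishes, as the palpation-only rows show. That also stands. An interaction test is no remedy. With half the slope under ultrasound its power was only 14–20%. With depth irrelevant under ultrasound it was 18%, 39% and 61% at the three slopes. Effect modification is not among the stated objectives, so its absence is no defect.

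**Conclusion.** The point holds as one of efficiency and prespecification. A baseline value already being collected, and plausibly prognostic on the protocol's own reasoning, has no stated place in the comparison of arms.

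With 40 per arm and an assumed log-odds effect of 1.4, adjustment gains about 0–2 points of power if depth is weakly prognostic or matters only under palpation. The gain is about 1–6 points if its slope is halved under ultrasound, and about 8–12 points if it is strongly prognostic in both arms (0.9–1.3 per SD). If depth is not prognostic, the loss is about half a point (82.2% vs 81.7%), within simulation error.

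The success rates and slopes are all assumptions. The 8–12 point range is the favourable end and should not be quoted as the expected gain. The case for change rests on a possible gain at almost no cost, not on any fault in the validity of the present test.

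**What to change.** State in the Statistical Analysis Plan section that the primary analysis of Substudy 2 is a logistic regression of first-attempt success on arm and radial skin-to-artery distance, with distance kept continuous. Report the technique effect as a risk difference standardised over all randomised patients, with a 95% CI, because the adjusted odds ratio is conditional on depth and not directly comparable with the unadjusted one. Keep the chi-square or Fisher's exact test as supportive, and say which result governs the conclusion. Specify that the distance is recorded before allocation is known, and which wrist's value is used.

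An arm-by-distance interaction may be added, labelled exploratory; it is optional. The cost is wording only: no new measurement, no more patients and no change to any procedure. The change should be made before outcome data are examined.

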2. To evaluate the safety and effectiveness of ultrasound-guided radial artery catheterization compared to traditional blind-palpation method
3. To compare the effectiveness of high-flow nasal cannula and facemask in the preoxygenation of general anesthesia
4. To compare the effect of different volatile anesthetics and M-Entropy guidance on the postoperative recovery in obese patients.

Study Protocol

The investigators will conduct a clinical trial using permuted block randomization and conforming to the CONSORT Statement^{49,50} to investigate multiple clinical outcomes in obese patients undergoing LSG at Shuang Ho Hospital, Taipei Medical University, New Taipei City, Taiwan. Three randomizations will be conducted, including radial artery catheterization using ultrasound guidance or blind palpitation, preoxygenation using HFNC or conventional facemask, and volatile anesthesia with desflurane or sevoflurane with or without M-Entropy guidance. A computer-generated list of randomizations (Research Randomizer, www.randomizer.org) will be used for these group allocations.

The flow diagram for research conduction is shown in Figure 2. Before surgery, every participant will undergo echocardiography to rule out severe cardiopulmonary disease (LVEF < 40% or moderate-to-severe pulmonary hypertension or confirmed diagnosis of coronary artery disease)

Substudy 1. Exploring potential risk factors of difficult intubation using ultrasound: A prospective single-blind cohort study

Before surgery, all enrolled patients will be examined for appearance features regarding difficult airway, including interincisor distance (< 3 cm or not)⁵¹, mentohyoid distance, thyromental distance (< 6.5 cm or not)⁵², neck movement (< 80 degrees or not)⁵³, neck circumference measured at the thyroid cartilage (> 43 cm or not)²⁸, modified Mallampati score⁵⁴, upper lip bite test⁵⁵, and mandibular prognathism test⁵⁶. Besides, ultrasound will be used to assess upper airway anatomy, including pretracheal soft tissue depth²⁷ and height and width of tongue base⁵⁷. Regarding pretracheal soft tissue depth, the distance from the skin to the anterior aspect of the trachea will be measured at three levels: vocal cords, thyroid isthmus, and suprasternal notch.²⁷ The amount of soft tissue at each zone is calculated by averaging the amounts of soft tissue in millimeters obtained in the central axis of the neck and 15 millimeters to the left and right of the central axis.

[figure not shown]

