Figure 2: Flow diagram for research conduction

Moreover, the increased tongue volume and deposition of fat at the base of tongue in obese people has been shown to be highly associated with risk of obstructive sleep apnea.⁵⁸ To measure the anatomy of tongue base, with the patient in a seated position, the convex transducer in the frequencies 1.5 to 5.0 MHz (GE C1-5-RS, GE Healthcare, Chicago, IL, USA) of a portable ultrasound device (LOGIQ™, GE Healthcare, Chicago, IL, USA) will be introduced to the skin of the neck in the submental region coronally, immediately cephalad to the body of the hyoid bone, and then in the area between the hyoid bone and the symphysis of the mandible. The patients will be instructed to avoid tongue movements, swallowing, or talking.⁵⁷ Maximal width of tongue base, tongue base height, and maximal height of mid-tongue will be measured.

The same anesthesiologist will perform all ultrasound measurements before surgery. Upon arrival at operating room, patients will be initially placed in a ramped position and then moved into a reverse Trendelenburg position to achieve a 30-degree incline of the thorax before preoxygenation. After induction of anesthesia, another anesthesiologist, blinded to all preoperative evaluation, will perform all laryngoscopies in this study. The laryngoscopy intubation will be performed using a size-3 or -4 Macintosh (Rüsch Inc., Duluth, GA, USA) blade and a styled endotracheal tube. The laryngoscopic view will be graded according to Cormack and Lehane's classification with external laryngeal pressure applied.⁵⁹ Laryngoscopy views graded as III or IV are defined as difficult. In case of failed direct laryngoscopy despite external laryngeal manipulation in the first attempt, video-assisted laryngoscope GlideScope® (Verathon Medical, Bothell, WA, USA) will be used as an intubation rescue technique. The video-assisted laryngoscope will be kept on standby at the operating room before induction. The correct placement of the endotracheal tube will be confirmed by capnography. Primary outcome is occurrence of difficult laryngoscopy. Secondary outcomes are first-attempt success rate and time to successful intubation.

Substudy 2. Radial artery catheterization using ultrasound guidance or blind palpation: An open-label randomized controlled trial

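### Substudy 2 does not keep the choice of resident independent of the open-label allocation, and its primary test takes no account of the operator

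*Combined protocol and SAP*

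**What the plan says.** **Operators (Study Protocol, Substudy 2).** "All radial artery catheterizations will be performed by trained year 1 or 2 anesthesiology residents with similar levels of experience"; the sentence then names the two techniques. The criterion that follows is "All residents have performed at least 5 blind-palpation and 5 ultrasound-guided radial arterial catheterizations prior to the study". This is a minimum. The text gives no upper limit, no number of residents, no plan to record experience, and no rule for matching a resident to a patient.

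**Outcome (same section).** "Primary outcome is first-attempt success rate, and secondary outcomes comprise time to successful arterial catheterization, number of attempts, sites and catheters used". An attending supervises and takes over after a set number of tries or a set time.

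**Allocation and masking.** The substudy title reads "Radial artery catheterization using ultrasound guidance or blind palpation: An open-label randomized controlled trial". There are 40 patients per arm. Under Study Protocol, "A computer-generated list of randomizations (Research Randomizer, www.randomizer.org) will be used for these group allocations", in permuted blocks. No stratum for operator or training year is named, and the text does not say when the arm becomes known relative to the choice of resident.

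**Analysis (Statistical Analysis Plan).** Outcomes "will be compared between two groups using chi-square tests" or Fisher's exact test when they are categorical. A separate clause provides multivariable logistic regression to look for factors that influence outcomes. It lists no covariates and does not mention operator, training year or clustering.

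**The concern.** First-attempt success is measured on the patient but produced by the operator. Randomising patients balances the patients. It balances operators only if the resident is chosen without regard to the arm. Here two training years are mixed, the experience criterion has no ceiling, and the technique is visible to everyone in the room. If whoever assigns the resident knows the arm and tends to send the more capable resident to the technique thought harder, the comparison of techniques is partly a comparison of residents. The stated test could not separate the two, and no later analysis could do so if operator identity was never recorded.

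The protocol does control the operator elsewhere. In Substudy 1 one anesthesiologist makes all the ultrasound measurements and a second, blinded one performs all the laryngoscopies. Substudy 2 has no comparable safeguard.

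**Working it through.** **1. The plan's own figure.** The only sample-size calculation is for Substudy 3: difference 30 s, SD 46 s, two-sided alpha 5%, power 80%. n = 2 × (1.960 + 0.842)² × 46² / 30² = 2 × 7.85 × 2116 / 900 = 36.9, so 37 per group, as stated. Substudy 2 has no calculation; its 40 per arm comes from the total of 80.

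**2. What 40 per arm can detect.** Using the normal approximation for two proportions (pooled variance under the null), the difference detectable with 80% power is about 31, 30, 27 or 24 points if palpation succeeds in 40%, 50%, 60% or 70%. These success rates are assumptions; the documents give none.

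**3. Bias if resident choice follows the arm.** Let g be the gap in first-attempt success between more and less skilled residents, and s the difference between arms in the share of patients treated by the more skilled. With no true effect of technique, the spurious difference is s × g. Example: shares 70% and 30%, success 70% and 50%. One arm has 0.7 × 0.70 + 0.3 × 0.50 = 0.64, the other 0.3 × 0.70 + 0.7 × 0.50 = 0.56. The difference is 0.08 = 0.4 × 0.2.

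**4. Type I error of the unadjusted chi-square test.** 40 per arm, mean success 60% (assumed), exact binomial calculation:

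| Share gap | Skill gap | Spurious difference | Type I error |
|---|---|---|---|
| 0 | any | 0 | 5.2% |
| 20 points | 10 | 2 points | 5.6% |
| 20 points | 20 | 4 points | 6.8% |
| 20 points | 30 | 6 points | 8.8% |
| 40 points | 10 | 4 points | 6.8% |
| 40 points | 20 | 8 points | 11.6% |
| 40 points | 30 | 12 points | 20.0% |

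Against the detectable 27 points at 60% success, 2 to 12 points is 2/27 = 7% to 12/27 = 44%.

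**5. Adjustment for training year.** In the six steered settings above, with the skill gap lying between training years, a test stratified by training year brought simulated type I error back to about 5%.

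**6. No steering.** With 8 operators (assumed) assigned independently of arm, the unadjusted test rejected in about 5.0% to 5.8% of null trials at between-operator SDs of 0 to 1.5 logits. Its level is sound.

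**7. Power of adjusted analyses without steering.** Same assumed 8 operators, no trend in skill over time. A random-intercept logistic model lost no power at SD 0 to 0.5. At SD 1.0 to 1.5 it gained about 5 to 9 points; a repeat of 1,000 trials per setting (10 patients per operator, log odds ratio 1.3) gave gains of about 3 and 8 points (61% to 64%, 51% to 60%). Mantel-Haenszel stratification on all 8 operators moved power from 79% to 76% at SD 0.5, 71% to 73% at SD 1.0, and 58% to 64% at SD 1.5.

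**The case against.** The strongest reply is that the bias is hypothetical. Open-label describes masking; it does not say when the allocation is disclosed or who is on the roster. Nothing in the documents shows residents being picked by arm, and the flow diagram, which is not reproduced in the text available here, might show the sequence. This stands: the documents leave the link open but do not show that it exists.

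Second, the sentence on experience can be read as saying that each resident is about equally practised in the two techniques, which the equal minimum of five and five fits. That also stands, so the sentence should not be treated as a failed claim that residents are alike. On either reading, a minimum does not secure similarity, and the gap in assignment and analysis remains.

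Third, the regression clause permits operator as a covariate. It does, but as a search for influential factors, with no covariates named and no place in the primary comparison. Operator is also not a listed data item.

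Fourth, the attending's takeover limits prolonged trying. It comes after the first attempt has failed, so it does not equalise first-attempt skill.

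A reader might also object that Objective 2 speaks of ultrasound guidance in general while only junior residents perform it. The Substudy 2 section states the operator population openly, and no planned conclusion claims more. That is a matter of wording and forms no part of this point.

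**Conclusion.** The point holds as a design improvement. The primary outcome depends on the resident making the first attempt, the text does not separate the choice of resident from the allocation, and the stated test ignores the operator. That dependence is an inference from who performs the procedure; the documents do not quantify it.

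A reader might infer that the comparison is biased, or that the chi-square test is invalid. The documents support neither. If residents are assigned independently of arm, the planned test keeps a type I error of about 5%, and ignoring the operator costs power only when residents differ substantially.

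If assignment did follow the arm, the spurious difference would be 2 to 12 points and type I error about 5.6% to 20%. Those ranges rest on an assumed skill gap of 10 to 30 points, an assumed share gap of 20 to 40 points and an assumed mean success of 60%. The upper end needs both gaps to be large. The change is worth making because it needs no extra patients and because unrecorded operator identity may not be recoverable afterwards.

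**What to change.** - **Assignment.** State that the resident for each case is named and logged before the Substudy 2 allocation is opened. This is the main protection, because it also covers differences in skill that no recorded variable captures.
- **Data.** Record operator (coded) and training year for every cannulation.
- **Analysis.** Make the primary comparison of first-attempt success a logistic model with treatment arm and a training-year term, an operator random intercept, or both, chosen in advance. Keep the unadjusted chi-square or Fisher's exact test as a sensitivity analysis. A training-year term does not adjust for differences within a year, and a random intercept only partly corrects for steering, so neither replaces the assignment rule.
- **Avoid** fixed stratification on every operator. In the simulation it cost 3 points of power (79% to 76%) when operators differed little.

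The cost is one scheduling rule, two data fields and one or two model terms. Sample size and patient care are unchanged.

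### Substudy 2: an unblinded supervisor's judgment sets how long a first attempt may last, and the plan has no common rule for when that attempt ends or how a takeover is scored

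*Combined protocol and SAP*

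**What the plan says.** All of this is in Study Protocol, Substudy 2, unless noted.

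- **Design.** The title is "Radial artery catheterization using ultrasound guidance or blind palpation: An open-label randomized controlled trial". Allocation is 1:1 with 40 patients per arm.
- **Outcomes.** "Primary outcome is first-attempt success rate, and secondary outcomes comprise time to successful arterial catheterization, number of attempts, sites and catheters used".
- **Attempt.** "An attempt is defined as a new penetration of the skin with the needle, followed by an unlimited number of subcutaneous needle redirections".
- **Who sets the time.** The rule, quoted up to its last word (site), reads: "Clinical judgment by the supervising anesthesiologist is used to determine the time allowed for an attempt, number of attempts allowed, and changes to a new".
- **Outer limits.** The next sentence reads: "The attending anesthesiologist will take over arterial cannulation if residents perform for more than 3 times or > 15 minutes".
- **Operator.** Year 1 or 2 residents are said to do every catheterization, yet the attending may step in as second operator.
- **Clock.** Timing starts with the probe on the wrist in the ultrasound arm and with the finger on the wrist in the palpation arm. It ends in both arms when the catheter is in place.
- **Recorder.** No independent or blinded recorder is named. Substudy 3, by contrast, has a blinded nursing anesthetist measure its outcomes.
- **Test.** The Statistical Analysis Plan section allows chi-square or Fisher's exact test for categorical outcomes, at two-sided 0.05.

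**The concern.** The definition of an attempt has no built-in end. While the needle stays under the skin, redirection can continue, so whether a slow first attempt finishes as a success or a failure depends partly on how much time it is given. That time is set by someone who knows the technique in use and who may expect one technique to do better. Shorter patience in one arm lowers that arm's first-attempt success, and longer patience raises it. The decision comes after allocation, so randomization does not protect against it. The number of attempts and of catheters used would be affected too.

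Takeover raises a second question. If the attending takes over through the same puncture, no new skin penetration has occurred. Read literally, a catheter then placed by the attending still belongs to the first attempt. The plan does not say whether it counts as a success.

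**Working it through.** **1. The plan's own figure.** The only sample size in the document is for preoxygenation (Substudy 3): difference 30 s, SD 46 s, type I error 5%, power 80%. The formula n = 2(1.96 + 0.84)² × 46² / 30² gives about 37 per group, as stated. It does not concern Substudy 2, for which no success rate, target difference or power is given.

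**2. How the rules fit together.**

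| Item | Judgment sentence | Limits sentence | Left open |
|---|---|---|---|
| Time | supervisor decides, per attempt | takeover after > 15 minutes | per attempt or in total; which governs |
| Number of attempts | supervisor decides | takeover after more than 3 times | which governs |
| Operator | – | attending takes over | scoring if this happens during the first puncture |

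The limit on number cannot affect first-attempt success, because it applies only after the first attempt is over. The time limit can, but only if it is reached during the first puncture.

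**3. Weight of one patient.** With 40 per arm, one reclassified patient moves that arm's rate by 1/40 = 2.5 percentage points. Take 24/40 in both arms and move patients from success to failure in one arm, with z = |difference| / √[p(1 − p) × 2/40] and p the pooled rate:

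- 8 moved (24 v 16): 0.200 / √(0.5000 × 0.5000 × 0.05) = 1.79, not significant.
- 9 moved (24 v 15): 0.225 / √(0.4875 × 0.5125 × 0.05) = 2.01, significant.

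Fisher's exact test needs 10.

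**4. False-positive rate under one-sided early stopping.** Assume equal true success p in both arms, and that a share s of would-be first-attempt successes is cut short in one arm only, so that arm's observed rate is p(1 − s). The probability of p-value < 0.05 is summed over all pairs of binomial counts (n = 40 each).

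| p | s | Rates compared | Chi-square | Fisher |
|---|---|---|---|---|
| 60% | 0 | 60 v 60 | 5.2% | 3.0% |
| 60% | 10% | 60 v 54 | 9.0% | 5.7% |
| 60% | 20% | 60 v 48 | 20.3% | 14.5% |
| 60% | 30% | 60 v 42 | 38.6% | 30.2% |
| 40% | 20% | 40 v 32 | 11.4% | 7.5% |
| 50% | 20% | 50 v 40 | 15.7% | 10.8% |
| 70% | 20% | 70 v 56 | 25.4% | 18.7% |
| 80% | 20% | 80 v 64 | 35.5% | 27.5% |

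Both p and s are assumptions, since the documents give neither.

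**5. Only a difference between arms matters.** If both arms lose 10% (54 v 54), chi-square rejects in 5.6% of trials, close to nominal.

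**The case against.** Four points can be made for the plan.

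- **The supervisor does not decide the outcome.** A reader might infer that this person can set the primary outcome at will. The documents do not support that. The end point is a catheter successfully placed, which judgment alone cannot bring about. Nor is the supervisor the only one who ends an attempt: a resident who withdraws and punctures again has ended the first attempt observably.
- **The two sentences need not contradict each other.** It is tempting to call the limits a conflict. They can be read together as judgment within an outer bound at which the attending takes over.
- **Blinding is not feasible.** The operator and supervisor must see the technique, and supervision of residents is part of care.
- **The illustration is hypothetical.** It puts all early stopping in one arm, and nothing in the documents suggests that this would occur. Fisher's exact test gives smaller figures than chi-square.

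All four stand, and they narrow the point without removing it. Even on the reading of judgment within a bound, discretion during the first attempt has no criterion common to both arms. Because blinding is not available, an objective scoring rule is the main safeguard left. The inflation also appears with Fisher's exact test.

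**Conclusion.** The concern holds in a limited form. The stated rule leaves the primary outcome of Substudy 2 open to different handling by arm: an unblinded supervisor can turn a continuing first attempt into a failure or prolong its chance of success. The limits overlap with that judgment. Their precedence, the basis of the time limit and the scoring of a takeover during the first puncture are unstated. This is an unreconciled ambiguity and not a proven contradiction.

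The size depends on behavior that cannot be known in advance. If 20% of would-be successes were cut short in one arm only, the false-positive rate would be 11.4% to 35.5% by chi-square and 7.5% to 27.5% by Fisher's exact test, for assumed true success of 40% to 80%. These figures show sensitivity and do not predict bias. As the plan stands, the bias could not be assessed afterwards, because nothing requires a record of who ended an attempt or why. The change should be made, and it is inexpensive.

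**What to change.** 1. **Reconcile the passages** on attempt limits, operator and takeover: which rule governs, whether the time is per attempt or in total, and how the statement that residents do every catheterization fits with a second operator. Clinical decisions stay with the supervisor, and no clinical limit is proposed here.

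2. **Define the outcome for scoring only.** Suggested wording: *First-attempt success is placement of the catheter by the resident, with the allocated technique, through the first skin puncture, within a scoring window that is the same in both arms, fixed before the first patient is enrolled, and timed from first skin puncture. Takeover or change of technique during the first puncture is scored as failure.* Timing from puncture matters because the protocol's present start events differ by arm.

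3. **Record** who ended each first attempt, when and why, preferably through someone other than the operator and supervisor.

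4. **Bound what remains.** The common window and the takeover rule deal with prolonged attempts and attending rescue. Scoring supervisor-ended attempts as failures in the main analysis does not remove early-stopping bias: a 60 v 48 split would still reject in about 20% of trials by chi-square. Report the number of such attempts by arm, and repeat the comparison scoring them as successes in both arms, then in each arm separately.

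**Cost.** Protocol wording and a few more fields on the cannulation form. Slow successes beyond the window count as failures, so the stated success rates may be slightly lower.
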